9.2. Description of Study Assessments

All assessments will be conducted according to the schedule presented in Table 2. Assessments may be repeated if requested by the medical monitor.

9.2.1. Medical History

Medical history will be collected by subject interview. Additionally, medical history deemed related to the subject's Fabry disease will be identified in the subject's medical records by the investigator or designee for entry into the appropriate eCRF, including, but not limited to such things as past serum creatinine results.

Since subjects will have participated in a previous migalastat study, historical medical history (ie, events or conditions that had their onset at least 90 days prior to Visit 1) will be considered as medical history for this study.

9.2.2. Safety Assessments

9.2.2.1. Adverse Events and/or Serious Adverse Events

Throughout the study, subjects will be given an opportunity to report AEs. The definitions, reporting, and monitoring of AEs and SAEs are described in Section 10.

9.2.2.2. Clinical Laboratory Tests

9.2.2.2.1. Safety Laboratory Tests

Samples for chemistry, hematology, and urinalysis are outlined in Table 4. Laboratory samples collected on a dose administration day will be collected predose.

Chemistry	Hematology	Urinalysis
ALT	Hematocrit	Color
Alkaline phosphatase	Hemoglobin	Appearance
AST	Platelet count	Specific gravity
Albumin	RBC count	рН
Bilirubin, total	WBC count (absolute)	Albumin
BUN	Automated WBC differential	Bilirubin
Calcium, total	Basophils	Blood
Carbon dioxide, total (bicarbonate)	Eosinophils	Glucose
Chloride	Lymphocytes	Ketones
СРК	Monocytes	Microalbumin
Creatinine, serum	Neutrophils	Microscopy of sediment
GGT		Nitrite
Glucose		Protein
Lactate dehydrogenase		WBCs
Magnesium		
Phosphorous		
Potassium		
Protein, total		
Sodium		
Uric acid		

Table 4:Clinical Laboratory Parameters

Abbreviations: ALT = alanine transaminase; AST = aspartate transaminase; BUN = blood urea nitrogen; CPK = creatine phosphokinase; GGT = gamma-glutamyltransferase; RBC = red blood cell; WBC = white blood cell

Safety laboratory tests will be performed at a central laboratory. Instructions for the collection, processing, and shipment of clinical laboratory samples will be provided in the Laboratory Manual.

The investigator or a designee will review laboratory results and assess any out-of-range laboratory results as "not clinically significant" or "clinically significant." Any results that are considered clinically significant may be confirmed in a repeat test at the investigator's discretion. The investigator should consider repeat testing of persistent clinically significant results until the analyte returns to normal levels or until an etiology is determined. The investigator or a designee will sign and date all laboratory reports.

Clinically significant laboratory abnormalities must be captured as AEs or SAEs, as appropriate.

9.2.2.2.2. Other Laboratory Tests

Urine pregnancy tests will be performed for all female subjects of childbearing potential (as defined in Section 8.4); date of last menstrual period, as applicable, will be recorded during telephone contacts.

Any subject who has a positive urine pregnancy test result should have a serum pregnancy test performed as soon as possible for confirmation. Any subject who becomes pregnant must discontinue study drug. Procedures for pregnancy reporting are described in Section 10.5.1.

9.2.2.3. Vital Signs

Vital signs include blood pressure (systolic and diastolic), respiration rate, heart rate, and body temperature. Measurements are to be taken with the subject in a sitting or supine position after having rested for 5 minutes, and the same position should be used at all visits. Blood pressure should be obtained using the same arm for all measurements.

9.2.2.4. Physical Examination

Complete physical examinations will include assessment of head/eyes/ears/nose/throat, skin, thyroid, neurological system, lungs, cardiovascular system, abdomen (liver and spleen), lymph nodes, and extremities.

9.2.2.5. Body Weight and Height

Body weight (kg) must be measured with the subject's shoes and clothes (except underwear) removed and will be rounded to 1 decimal place. The same scale should be used for individual subjects throughout the study and scales should be calibrated periodically throughout the study to ensure accuracy of measurement.

Height (cm) must be measured with the subject's shoes removed.

9.2.2.6. Electrocardiograms

A standard 12-lead electrocardiogram (ECG) will be performed.

Subjects will rest for approximately 5 minutes before the ECG recording begins and will be in the supine position throughout the ECG evaluation. Electrocardiograms will be read centrally. Clinically significant findings not present before the start of treatment, which meet the definition of an AE, must be recorded in the eCRF.

9.2.2.7. Echocardiogram

Echocardiogram parameters considered for safety include left ventricular mass index (LVMi), ejection fraction, fractional shortening, left ventricular internal diameter end diastole and end systole, midwall fractional shortening, and wall thickness.

Echocardiograms will be read centrally.

9.2.2.8. Tanner Staging

Tanner Staging will be performed for all subjects.

Because reversible infertility was noted in nonclinical studies with male rats, Tanner Staging will be used to assess sexual development, ie, breast development (B1 to B5) and pubic hair development (Ph-1 to Ph-5) in females and pubic hair and genital development (G-1 to G-5) in males (see Appendix A).

9.2.2.9. Concomitant Medications and Procedures

Subjects will be asked to report any new or changes in previously reported prescription and non-prescription medications, including dosage, frequency, and administration dates. Information will be entered in the eCRF and source records. Information regarding any procedures performed since the last visit will also be collected.

9.2.3. Pharmacodynamic Assessments

Blood samples will be collected for measurement of lyso-Gb₃ levels in plasma, and analogues. In addition, to get a better understanding of early PD biomarkers for Fabry disease, samples may be used for exploratory cardiac biomarkers such as high sensitivity tropin and NT-proBRN. Plasma levels of lyso-Gb₃ will be measured using a validated liquid chromatography mass spectrometry (LCMS) assay.

9.2.4. Efficacy Assessments

9.2.4.1. Estimated Glomerular Filtration Rate

Estimated GFR will be calculated using the Schwartz formula according to the standards of the central laboratory. Subjects who reach the age of 18 and remain on study will continue to have eGFR calculated by this method by the sponsor at the time the value is entered into the database.

9.2.4.2. Urine Protein and Albumin Levels

Protein and albumin (or microalbumin) levels in urine (as part of urinalysis) will be measured.

9.2.4.3. Echocardiogram

The key echocardiogram parameter considered for efficacy is LVMi. In addition, ejection fraction, fractional shortening, left ventricular internal diameter end diastole and end systole, midwall fractional shortening, and wall thickness will be assessed.

Echocardiograms will be read centrally.

9.2.4.4. Subject Questionnaires

All questionnaires will be provided in a separate Patient Outcomes Manual.

9.2.4.4.1. Dosing Diary

Subjects are to record the date and time of each migalastat administration in the Dosing Diary provided in the dosing wallet containing their study drug. Subjects will be asked to complete diary entries in order to track migalastat administration beginning on Day 1 and for the duration of the study.

9.2.4.4.2. Fabry-Specific Pediatric Health and Pain Questionnaire

The Fabry-Specific Pediatric Health and Pain Questionnaire (FPHPQ) includes questions about Fabry disease-specific symptoms (eg, sweating, pain, dizziness and tiredness, heat and cold intolerance, swollen eyelids, gastrointestinal symptoms, feeling thirsty, difficulty hearing, ringing or buzzing noise in the ears, and ability and enjoyment to participate in sports). The frequency of these symptoms will be rated using a 5-point Likert scale (always, often, sometimes, seldom, never). Pain intensity is measured on a 10-point scale, numeric responses are given for onset of pain and school days missed, and yes/no questions are posed about difficulty hearing and other problems not specifically mentioned. There are 2 age-specific self-report versions for children 8 to 12 years and 13 to 18 years, respectively.

9.2.4.4.3. Pediatric Quality of Life Inventory

The Pediatric Quality of Life Inventory[™] (PedsQL[™]) is a modular approach to measuring health-related quality of life in healthy children and adolescents and those with acute and chronic health conditions. It consists of 23 items and includes questions about physical functioning, emotional functioning, social functioning, and school functioning relative to the prior 7 days, using a 5-point scale. Both parents or legally-authorized representatives and subjects complete the appropriate version of the PedsQL independently of one another. Parents or legally-authorized representatives and subjects may self-administer the questions after introductory instructions are given by study site personnel.

10. ADVERSE EVENTS AND SERIOUS ADVERSE EVENTS

Investigators and study site personnel are responsible for detecting, documenting, and reporting AEs and SAEs. For each subject, reporting of AEs and SAEs begins after written informed consent is provided.

10.1. Definitions

10.1.1. Adverse Event

An AE is defined as any untoward medical occurrence in a subject or clinical investigation subject administered a pharmaceutical product and which does not necessarily have a causal relationship with this treatment. An AE can therefore be any unfavorable and unintended sign, symptom, or disease temporally associated with the use of a medicinal product, whether or not considered related to the medicinal product.

Therefore, AEs include the following:

- The onset of new signs, symptoms, conditions, and illnesses
- Exacerbation of pre-existing conditions or illnesses
- Abnormal laboratory findings deemed clinically significant by the investigator
- Physical examination changes deemed clinically significant by the investigator
- Abnormal medical evaluation findings (eg, ECG) that are not documented at baseline and/or, in the investigator's opinion, represent a clinically significant change in the subject's health during study participation
 - Baseline medical evaluation findings (eg, ECG) that were not previously provided as medical history and can be determined as starting before baseline, are not considered AEs and will be recorded as medical history.

Adverse events will be recorded in the eCRF and subject's source record beginning from the time written consent (assent) is provided through the follow-up visit (at least 30 days after the last dose of study drug).

Subjects will be enrolling in this study following completion of Study AT1001-020. Therefore:

- Adverse events that are ongoing as of the last study visit of Study AT1001-020 will be entered in the AE eCRF.
 - The start date recorded in Study AT1001-020 will be the start date entered in the current study AE eCRF.
 - The event will be noted as continuing from Study AT1001-020 in the current study's AE eCRF.

A single diagnosis should be entered when known. If a clear diagnosis cannot be determined at the time of eCRF completion and the subject's source record entry, each sign and symptom must be recorded individually, until a final diagnosis is established. Conditions, signs, symptoms, etc that are present in the subjects' medical history at baseline should only be reported as AEs if they worsen (ie, increase in severity) since baseline.
Adverse events that begin after the first dose of investigational product in Study AT1001-036 will be considered treatment-emergent adverse events (TEAEs).

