5.4. Study Rationale

This is a Phase 3b, open-label, uncontrolled, multicenter study to evaluate the long-term safety, pharmacodynamics (PD), and efficacy of migalastat treatment in pediatric subjects over 12 years of age with Fabry disease and amenable *GLA* variants. The youngest pediatric subjects included in previous studies with migalastat were 16 years of age.

Early signs and symptoms of Fabry disease tend to manifest during childhood and adolescent years (ie, < 18 years), particularly in males with the classic phenotype, and are followed later in life by the development of overt kidney, cardiovascular, and central nervous system complications. In the 2 largest disease registries, the Fabry Outcome Survey and the Fabry Registry (Ramaswami, Whybra et al. 2006; Hopkin, Bissler et al. 2008), the median age of symptom onset is reported to be approximately 6 years in boys and 8 to 9 years in girls. Diagnosis is often delayed due to the different manifestations of the disease, its relative rarity, and the lack of clinical awareness of the condition, making the median age of diagnosis approximately 9 years in boys and 9 to 13 years in girls.

Data from these Fabry disease registries indicate that the most common symptom among pediatric subjects was neuropathic pain (eg, episodic pain crises, chronic pain, and acroparesthesia), which was reported more frequently by boys than by girls (58.8% versus 40.5%), and with an earlier age of onset (7 versus 9 years). The gastrointestinal tract was the

second most commonly involved organ system with 18% of children experiencing signs and symptoms (eg, abdominal pain and diarrhea); the median age at onset of symptoms was 5 years in boys and 9.5 years in girls. The next most common sign was skin findings such as angiokeratomas. As with neuropathic pain, these symptoms and signs were more prevalent in boys than girls and occurred at an earlier age of onset.

Renal involvement appears less commonly in the younger population; however, a limited number of older adolescents have been reported to have impaired glomerular filtration rate (GFR), proteinuria, and hyperfiltration, along with cardiac abnormalities, pain, and gastrointestinal symptoms.

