10.1.2. Serious Adverse Event

An SAE is any AE occurring at any dose that results in any of the following outcomes:

- death
- a life-threatening event
 - This includes any AE that in the view of either the investigator or sponsor places the subject at immediate risk of death. It does not include an AE that, had it occurred in a more serious form, might have caused death.
- requires inpatient hospitalization or prolongs existing hospitalization
 - Hospitalization signifies the subject has been admitted, regardless of duration, for observation and/or treatment that would not have been appropriate in a physician's office or outpatient setting.
 - Hospitalizations for elective or pre-planned treatment of a pre-existing condition do not have to be reported as SAEs if the following criteria are met:
 - the condition is documented in the subject's medical history and has not worsened since the informed consent form was first signed; and
 - the condition and planned procedure are documented in the subject's source records at baseline.
 - Emergency room/department or outpatient treatments that do not result in admission do not have to be reported as an SAE, unless another SAE criterion is met. Events assessed and treated in these circumstances should be captured as AEs in the eCRF and documented in the subject's source records.
 - Hospitalizations solely based on subject logistics (eg, subject is admitted due to limited hospital accessibility for what would otherwise be an out-subject procedure) do not have to be reported as SAEs provided that the hospitalizations are clearly defined as such in the subject's source record.
- persistent or significant incapacity or substantial disruption of the ability to conduct normal life functions
- congenital anomaly/birth defect

An important medical event that does not result in one of the above serious outcomes may be considered an SAE when, based upon appropriate medical judgment, it may jeopardize the subject and may require medical or surgical intervention to prevent one of the listed serious outcomes. Examples of such medical events include allergic bronchospasm requiring intensive treatment in an emergency room or at home, blood dyscrasias, or convulsions that do not result in inpatient hospitalization, or development of drug dependency or drug abuse.

If the following 4 elements are known, the event must be reported as described in Section 10.4.2:

- identifiable subject
- event term
- study drug

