- identifiable reporter

Additionally, the investigator's assessment of an event's relationship to study drug (see Section 10.2) is essential for Amicus to appropriately process the report and must be included.

Subjects and parents or legally-authorized representatives must be informed and understand that they should report events meeting the definition for SAE to study site personnel as soon as possible (and not wait until their next study visit).

If a non-serious event becomes serious, the change in status must be appropriately entered in the eCRF and the subject's source record, and reported to Amicus as described in Section 10.4.2.

If the investigator becomes aware of an SAE that occurs more than 30 days after the last dose of study drug, and considers the event possibly, probably, or definitely related to study drug, the investigator should contact the medical monitor (see Table 1) or the Clinical Operations Lead to determine how the SAE should be documented and reported.

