10.3. Severity Assessment

The investigator or a qualified sub-investigator will review each event and use the following definitions for rating intensity:

- Mild: awareness of sign, symptom or event, but the AE is easily tolerated and does not interfere with daily activity
- Moderate: discomfort enough to cause interference with usual activity and may warrant intervention, but the subject is still able to function
- Severe: incapacitating with inability to do usual activities or significantly affects clinical status, and requires medical intervention

It is important to distinguish the difference between events that meet the definition of serious and events that are deemed as severe in intensity. Adverse events assessed as severe in intensity are not SAEs unless at least 1 of the definitions in Section 10.1.2 is met. Adverse events of any intensity must be reported as SAEs if at least 1 definition in Section 10.1.2 is met.

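### Protocol 10.1.1 gives two conflicting rules for when a pre-existing condition is an AE, and the narrower one gives no route to report greater frequency or duration at unchanged intensity

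*Protocol*

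**What the plan says.** Protocol 10.1.1 opens with a broad definition of an AE and a list of what it includes. One item is "Exacerbation of pre-existing conditions or illnesses", with no limit on how the exacerbation shows itself. Near the end of the section, a rule for conditions, signs and symptoms in the medical history at baseline says they "should only be reported as AEs if they worsen (ie, increase in severity) since baseline".

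Protocol 10.3 supplies the meaning of severity. The investigator "will review each event and use the following definitions for rating intensity", and the three grades (mild, moderate, severe) turn on how well the event is tolerated and how far it interferes with activity. Frequency and duration appear in none of them. The section then separates intensity from seriousness: "It is important to distinguish the difference between events that meet the definition of serious and events that are deemed as severe in intensity".

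Protocol 10.1.2 builds the SAE on the AE: "An SAE is any AE occurring at any dose that results in any of the following outcomes". It exempts certain admissions for pre-existing conditions, and it asks that emergency or outpatient treatment without admission be captured as AEs.

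The counts feed the first of the eight safety endpoints in Protocol 11.1.1 (TEAEs, SAEs, and AEs leading to discontinuation). SAP 9.2 adds an incidence rate: total events divided by total patient-years of exposure.

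**The concern.** The two rules in 10.1.1 cannot both be followed for a history condition that gets worse in any way other than intensity. The closing sentence is the more specific of the two. *Only* makes it exclusive, and *ie* makes the reference to severity a definition and not an example. A site could reasonably treat it as controlling.

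The class of conditions it governs is wide. Protocol 9.2.1 treats events and conditions with onset at least 90 days before Visit 1 as medical history, so long-standing Fabry symptoms fall under it. Protocol 5.4 describes neuropathic pain as the most common pediatric symptom and includes "episodic pain crises, chronic pain, and acroparesthesia" among its forms. For symptoms that come and go, a rise in frequency or duration is a natural form of worsening.

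At stake are the AE counts in an uncontrolled study whose primary objective is long-term safety. No comparator arm would reveal an under-count, and the error runs in the drug's favor.

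**Working it through.** No figure in the plan can be reproduced here. The check sets the passages side by side and applies each to the same cases.

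| Change after baseline | Exacerbation item, 10.1.1 | Closing sentence, 10.1.1 | Other text |
|---|---|---|---|
| History condition rises from mild to moderate | AE | AE | None needed |
| Same grade, more frequent | AE, if judged an exacerbation | Not an AE | None |
| Same grade, longer episodes | AE, if judged an exacerbation | Not an AE | None |
| Already severe, more frequent or longer | AE, if judged an exacerbation | Not an AE: 10.3 has no higher grade | None |
| Same grade, emergency treatment, no admission | AE, if judged an exacerbation | Not an AE | 10.1.2: capture as an AE |
| Same grade, unplanned admission | AE, if judged an exacerbation | Not an AE | 10.1.2: not among the exempted admissions |

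**Frequency and duration (rows 2 to 4).** The two rules give opposite answers, and nothing else in the documents settles which applies.

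**Seriousness (rows 5 and 6).** Read literally, the closing sentence stops the event from being an AE, and an SAE must first be an AE. The surrounding text points the other way:
- The hospitalization exemption in 10.1.2 requires elective or pre-planned treatment, a condition that has not worsened since consent, and baseline documentation of both condition and procedure. A further exemption covers purely logistical admissions. Neither covers an unplanned admission, and the first would have little purpose if unchanged history conditions could never give an SAE.
- Section 10.3 says "Adverse events of any intensity must be reported as SAEs if at least 1 definition in Section 10.1.2 is met".
- Section 10.1.2 says "If a non-serious event becomes serious, the change in status must be appropriately entered in the eCRF".

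The last two begin from an event already recognized as an AE or already recorded, so they do not fully close the gap. The result for seriousness is ambiguity, not exclusion.

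**Effect on the planned summaries.** Let E be the treatment-emergent events under the broad rule, u those left out under the narrow one, and PY the patient-years.
- Event rate: the reported value is (E − u)/PY, a shortfall of u/PY. PY does not change, so any u > 0 lowers the rate.
- Subject incidence: SAP 9.2 counts a subject once within each SOC and preferred term. A percentage falls only where the omitted event was that subject's only one in the category.

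**Size of u.** It cannot be obtained. The documents give no baseline symptom counts and no episode rates. They also do not say whether a worsened recurrent condition is entered once or once per episode, so even a known number of extra episodes would not fix u. Protocol 5.4 gives registry figures (neuropathic pain in 58.8% of boys and 40.5% of girls; gastrointestinal signs and symptoms in 18% of children). These show that such conditions are common in the disease; they do not describe the subjects of this study.

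**The case against.** The best defense is that the section should be read as a whole. The general definition covers any untoward occurrence, the exacerbation item is unrestricted, and a site following either could report more frequent or longer episodes. The grades in 10.3 refer to interference with activity, so an investigator who grades the condition overall might raise the grade when episodes become more frequent. The FPHPQ rates symptom frequency and records school days missed at the 6-monthly visits, and SAP 7.3.1 summarizes its change from baseline, so worsening would not go unseen. Protocol 10.4.1 leaves detail to the eCRF Completion Guidelines, which are not among the documents and may already clarify the point.

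Much of this stands, and it limits the point. A reader might infer that such episodes, including newly serious ones, are never counted. The documents do not support that: the exacerbation item gives a route for the first kind, and 10.1.2 and 10.3 point toward reporting the second. A reader might also infer that a primary safety endpoint is affected, or that most subjects are. Safety is the primary objective, but no safety endpoint is labelled primary, and the share of subjects with such histories is not given.

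What the defense does not do is remove the conflict. Section 10.3 has the investigator rate each event, so overall grading is possible but not stated. The FPHPQ is an efficacy measure and does not enter the AE counts.

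**Conclusion.** The point holds as an internal contradiction with a likely direction of bias. Protocol 10.1.1 both includes any exacerbation of a pre-existing condition and limits history conditions to a rise in intensity. Where sites follow the limit, increases in frequency or duration at unchanged intensity go unreported, as does further worsening of a condition already at the top grade. TEAE incidence and the SAP event rate can then be too low. SAE capture is ambiguous in wording, although the intent to report unplanned admissions is reasonably clear.

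The size is unknown. The conclusion rests on two assumptions: that at least some sites treat the specific sentence as controlling, and that the eCRF Completion Guidelines do not already resolve it. The point deserves correction because the affected counts serve the primary objective and there is no control arm against which to judge them.

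**What to change.** Reconcile the two statements in Protocol 10.1.1. Keep the rule that history conditions are AEs only when they have worsened since baseline, but define worsening as an increase in severity, frequency or duration, or the meeting of any SAE criterion. This agrees with the exacerbation item and with 10.1.2.

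State whether a worsened recurrent condition is entered as one AE or one per episode; without this, the SAP event rate has no fixed meaning for such conditions. Because the TEAE definitions in Protocol 10.1.1 and SAP 9.2 both go by when an event begins, the entry should carry the date of worsening.

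Put the same wording in the eCRF Completion Guidelines. Protocol 14.1.8 allows a clarification memo ahead of an amendment, so the change need not wait. Ask sites to check medical-history conditions against the clarified rule for data already entered.

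The cost is one reworded sentence plus the entry rule, a matching guideline change, a small check at sites, and a somewhat higher AE count. No dose, treatment or clinical rule changes.
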